2. OBJECTIVES AND HYPOTHESES

2.1 Primary Objective(s) & Hypotheses

Objectives

- (1) To assess the feasibility of a patient educational program to improve germline genetic testing for eligible patients with prostate cancer.
- (2) To assess the effectiveness of a patient educational program with regards to increasing germline genetic testing rate among adult prostate cancer patients who are recommended to receive germline testing per NCCN guidelines.

Hypotheses

- (1) We hypothesize intervention will be feasible with successful recruitment of our target sample size.
- (2) We hypothesize that the rates of germline testing among patients recruited to the study will be higher than rates of testing among patients not enrolled in the study.

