3.2 Study Population

The target population for this study is patients older than 18, with prostate cancer who meet the NCCN criteria for germline testing and who have not undergone prior germline testing.

Subjects will include those patients seen at a facility in the UCSD Health System. Genitourinary oncology clinics will be screened 1 week in advanced for eligible patients. Recruitment procedures will also involve the review of subject records by designated study personnel (e.g., investigators and/or study coordinators) in order to identify potentially eligible subjects. Since Protected Health Information (PHI) will be accessed via the hospital's medical record database and scheduling system (e.g., EPIC/IDX) *prior* to contacting the potential subject about the research study, we have been granted a partial waiver of HIPAA authorization for access to PHI for purposes of prescreening only.

For patients who are eligible for the trial, the investigator will approach the subject and offer participation in the trial. Standard HIPAA authorization to collect research data from the subject's medical record will be obtained at the time of informed consent. Given the COVID-19 pandemic, we are conducting sessions both in clinic and virtually. This will primarily occur via video chat or telephone. Given that this is a low-risk intervention of an educational session, we believe that virtual consenting is also appropriate here given the current pandemic.

For patients who decline the intervention or have not been approached at the time of analysis, these patients will be considered a separate cohort for comparison to the intervention cohort.

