4.1.2 Definition of Comparison Exposure

The comparison group will include individuals with prostate cancer who meet criteria for germline testing however were not approached about participating in the intervention or were approached and declined participating in the educational intervention. In this context, germline testing education will be at the discretion of the treating medical team.

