4.2 Outcomes

Primary Endpoints

1. The proportion of patients who undergo germline testing among those who are enrolled to the study compared to the proportion of patients who undergo germline testing who were eligible, but not enrolled into this study during the study time period
2. Feasibility of implementing an educational intervention for men with prostate cancer at risk of having a hereditary cancer syndrome. This will be assessed by:
 - Accrual rate by month.
 - Proportion of patients who consent to educational intervention among those who are approached (stratified by whether consent was performed in-person or virtually).

Secondary Endpoints

1. Patient understanding of germline testing before and after the education intervention based on questionnaire responses.
2. Patient-reported opinions on germline testing before and after intervention, and patient-reported satisfaction after educational intervention based on questionnaire responses.
3. Physician responses regarding how the germline testing result changed patient management.
4. Prevalence of pathogenic germline mutations among study patients who undergo germline testing.

Exploratory Endpoints

1. Clinical factors (patient and family history, disease characteristics, and outcomes) that are associated with the presence of a germline mutation in a cancer susceptibility gene.

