4.4 Statistical Analysis Plan

4.5 Statistical Methods – General Aspects

4.5.1 Primary Objective(s): Calculation of Epidemiological Measure(s) of Interest (e.g. descriptive statistics, hazard ratios, incidence rates, test/retest reliability)

Primary Endpoints

With regards to the primary endpoint, at the completion of the study, the proportion of patients who complete germline testing among all who are enrolled to the study will be computed. A sample size of 50 patients produces a two-sided 95% confidence interval on the proportion with a width ranging from 0.27 to 0.29 when the observed proportion ranging from 0.3 to 0.7. For proportions, 95% confidence intervals will be calculated using the exact method.

We will also compute the proportion of patients who completed germline testing for all eligible prostate cancer patients evaluated in clinic but not enrolled into this study during the study period. Characteristics between these two groups will be compared using Fisher's Exacts or Wilcoxon Rank Sum tests. The proportion of patients who underwent germline testing in the intervention vs non-intervention cohorts will be compared using Fisher's exact test.

4.5.2 Secondary Objective(s): Calculation of Epidemiological Measure(s) of Interest (e.g. hazard ratios, incidence rates, test/retest reliability)

Secondary endpoints including germline mutation frequency, patient understanding of germline testing, and medical management from germline testing will be described using descriptive statistics such as bar graphs, box plots, percentages, means and standard deviations, etc.

4.5.3 Exploratory Objective(s): Calculation of Epidemiological Measure(s) of Interest (e.g. hazard ratios, incidence rates, test/retest reliability)

- Associations between clinical factors and pathogenic germline alterations will be evaluated using Odds Ratio.
- Impact of germline testing on prostate cancer and cancer surveillance management will be qualitatively described.

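### Primary endpoint 1 contrasts non-randomised cohorts using only an unadjusted Fisher's exact test, with no planned effect estimate or confidence interval for the difference

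*Combined protocol and SAP*

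**What the plan says.** Section 2.1 makes effectiveness a primary objective, with the hypothesis that "rates of germline testing among patients recruited to the study will be higher than rates of testing among patients not enrolled in the study". Section 4.2 turns this into primary endpoint 1, with the comparator being men who were "eligible, but not enrolled into this study during the study time period".

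The cohorts are formed by selection. Under sections 3.1 and 5.1.2 the treating physician must agree before a man is approached. Section 4.1.2 defines the comparator as men who "were not approached about participating in the intervention or were approached and declined participating in the educational intervention", and section 3.2 agrees: "For patients who decline the intervention or have not been approached at the time of analysis, these patients will be considered a separate cohort". Section 3.3 admits men by two routes: (a) very-low- to intermediate-risk disease that qualifies through family history or intraductal histology, and (b) high-risk, very-high-risk, node-positive or metastatic disease.

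The between-cohort analysis is all in section 4.5.1. A testing proportion is computed in each cohort. On intervals: "For proportions, 95% confidence intervals will be calculated using the exact method". On comparability: "Characteristics between these two groups will be compared using Fisher's Exacts or Wilcoxon Rank Sum tests". On the contrast itself: "The proportion of patients who underwent germline testing in the intervention vs non-intervention cohorts will be compared using Fisher's exact test".

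No section specifies stratification, regression, weighting, matching or a sensitivity analysis for this contrast. The odds ratio in section 4.5.3 concerns germline alterations, not testing uptake. Section 4.3 lists stage, sites of metastasis, family history and clinician as data to capture, but gives none of them a role in the primary analysis.

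**The concern.** Fisher's exact test answers whether two crude proportions differ. In a randomised comparison that is also a question about the intervention; here it is not. If the enrolled cohort holds a different share of, say, advanced disease, and men with advanced disease are tested more or less often whatever education they receive, the crude contrast contains that difference in case mix. The comparison of characteristics can reveal it, but no step follows. With 50 enrolled men, a non-significant comparison would not show balance either.

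The second gap is the missing effect measure. The sample size is justified by precision, yet that precision concerns the enrolled cohort alone. For the contrast that carries the primary hypothesis, no difference, ratio or interval is planned. Section 4.6.3 names recruitment bias as a key limitation, but its remedies all act at recruitment.

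**Working it through.** **1. The plan's own figure.** Sections 4.5.1 and 4.8 give a 95% interval width of 0.27 to 0.29 for n = 50 and observed proportions of 0.3 to 0.7. The Clopper-Pearson limits are the 0.025 quantile of Beta(x, n−x+1) and the 0.975 quantile of Beta(x+1, n−x). The widths are 0.2675 at 0.3 or 0.7, 0.2841 at 0.4 or 0.6, and 0.2895 at 0.5. The stated figure is reproduced. It describes one cohort and says nothing about the difference.

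**2. What an interval for the difference would show.** The documents give no comparator size or testing rate, so these are assumed: 50% of 50 enrolled against 30% of 50, 100 or 200 comparators. The Newcombe limits are d − √[(p1−l1)² + (u2−p2)²] and d + √[(u1−p1)² + (p2−l2)²], where l and u are the Wilson limits.

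| Comparators | Difference | 95% CI | Fisher p |
|---|---|---|---|
| 50 | 0.20 | 0.008 to 0.372 | 0.066 |
| 100 | 0.20 | 0.036 to 0.356 | 0.020 |
| 200 | 0.20 | 0.051 to 0.346 | 0.012 |

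**3. Case mix alone, no education effect.** Suppose there are two disease categories with testing rates a and b, the same in both cohorts. The first category makes up a share m1 of enrolled men and m2 of comparators. Each crude rate is m·a + (1−m)·b, so the crude difference is (m1−m2)(a−b). For a = 0.6, b = 0.2, m1 = 0.7 and m2 = 0.4:

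- enrolled: 0.7×0.6 + 0.3×0.2 = 0.48
- comparators: 0.4×0.6 + 0.6×0.2 = 0.36
- difference: 0.3×0.4 = 0.12

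Rejection probabilities come from full enumeration of the two binomials (two-sided 0.05, 50 enrolled). Every rate, mix and comparator size is assumed, as are the alpha and sidedness, which the plan does not state for this test.

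| a v b | m1 v m2 | Crude rates | Difference | Rejection, 50/100/200 comparators |
|---|---|---|---|---|
| 60% v 20% | 50% v 50% | 40% v 40% | 0 | 3/4/4% |
| 50% v 30% | 70% v 50% | 44% v 40% | +4 | 5/6/7% |
| 50% v 30% | 70% v 40% | 44% v 38% | +6 | 7/9/10% |
| 60% v 20% | 70% v 50% | 48% v 40% | +8 | 10/12/15% |
| 60% v 20% | 70% v 40% | 48% v 36% | +12 | 18/25/31% |
| 60% v 20% | 80% v 40% | 52% v 36% | +16 | 31/41/50% |
| 50% v 30% | 40% v 70% | 38% v 44% | −6 | 7/9/9% |
| 60% v 20% | 40% v 70% | 36% v 48% | −12 | 18/26/29% |

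**4. What stratification does.** The Mantel-Haenszel risk difference is Σ w(p1−p0) / Σ w over strata, with w = n1·n0/(n1+n0). Take the +12 row at its expected counts with 100 comparators: 21/35 and 3/15 tested among enrolled men, 24/40 and 12/60 among comparators. The crude difference is 24/50 − 36/100 = 0.12. The weights are 35×40/75 = 18.67 and 15×60/75 = 12. Both within-stratum differences are 0, so the stratified difference is 0.

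**5. Price in precision.** These are 20,000 simulations with zero effect and the Sato variance. They use three strata, with a mix of 10/20/70% enrolled against 30/30/40% comparators (assumed). Cells give 50/100/200 comparators.

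| Testing by stratum | Mean crude difference | Crude coverage | Stratified coverage | Crude width | Stratified width |
|---|---|---|---|---|---|
| 20/40/60% | 0.10 | 81/77/75% | 94/94/94% | 0.385/0.335/0.306 | 0.394/0.339/0.305 |
| 30/40/50% | 0.05 | 91/90/90% | 94/94/95% | 0.384/0.334/0.305 | 0.405/0.349/0.314 |
| 40/40/40% | 0.00 | 95/95/94% | 94/94/95% | 0.380/0.330/0.301 | 0.405/0.347/0.312 |

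The mean stratified difference is 0.00 in every row. The largest widening is 0.405 − 0.380 = 0.025, where stratum has no bearing on testing. Where it matters most, the widening is at most 0.394 − 0.385 = 0.009. With this mix, 64% of simulated studies had five or fewer enrolled men in some stratum and 0.5% had an empty one, which argues for two strata by default.

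**The case against.** The strongest objection is that the harm is assumed. No section says that disease category influences enrolment or testing, and all men in both cohorts meet the same guideline criteria. This stands. A reader might infer that the effectiveness result will be biased in favour of education; the documents support neither the existence nor the direction of such a bias.

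A reader might also infer that the plan yields nothing but a p-value and ignores bias. That goes too far. Section 4.5.1 gives both cohorts' proportions, its exact-interval sentence is general enough to cover each, and characteristics are compared. Section 4.6.1 adds rotating clinic screening, several modes of delivery and Spanish materials, and section 4.6.3 discloses the limitation. What is missing is narrower: an estimate and interval for the difference, and any step that acts on an imbalance.

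Next, the selection that the documents do describe is by physician and by willingness, not by disease category. This also stands. The simulations make category the only confounder, so the good performance of stratification in them is close to built in. They show what the method can remove, not that it removes the selection described.

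Finally, a fine stratification is not free. Route (b) in section 3.3 accepts high-risk, node-positive and metastatic disease alike, so eligibility alone does not separate them, and a man never screened may have no prescreening record. This limits the default to the two eligibility routes.

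That the study is a 50-patient pilot does not dispose of the point, because effectiveness is still a primary objective with a directional hypothesis.

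**Conclusion.** The point holds as a gap in the analysis plan, not as a demonstrated bias. A primary contrast between selected cohorts rests on an unadjusted test, with no effect estimate or interval for the difference and no protection if case mix differs.

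The consequence ranges from none to material. If either the mix or the testing rates are equal across categories, the crude difference is 0 and rejection stays at 3% to 4%. In the assumed scenarios with an imbalance, the crude difference runs from 4 to 16 points, its sign reverses when the mixes are swapped, and rejection runs from 5% to 50%. None of these inputs comes from the documents.

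The omission itself is certain from the text; its effect on this trial's result cannot be known in advance. The change is worth making because it is cheap and keeps the planned test. A reader should not infer that stratification would turn the contrast into a causal estimate: physician selection and self-selection remain.

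**What to change.** In section 4.5.1:

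- Report the risk difference with a 95% interval, crude and Mantel-Haenszel-stratified. Prespecify the stratified difference as the main effectiveness estimate and keep Fisher's test as supportive.
- Use the two eligibility routes in section 3.3 as strata. Split out metastatic disease only if stage is recorded for non-enrolled men and counts allow.
- Take the stratum from the medical record in the same way for both cohorts. The Family History Questionnaire is a poor source here: section 5.1.2 calls it standard in the programme, but section 3.1 and the assessment schedule place it at the education session.
- Report any stratum that is empty in one cohort, since it contributes nothing to the estimate.
- Show testing proportions separately for decliners and for men never approached, and add a clinician-stratified sensitivity analysis if the data allow.
- State that stratification does not remove physician selection or self-selection, so the estimate is not causal.
- Confirm that comparator data may be used. Section 3.2 describes the waiver as "for access to PHI for purposes of prescreening only", and the comparison already planned needs the same confirmation.

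The cost is wording, a little programming, and an interval up to about 0.025 wider in the assumed three-stratum scenarios when stratum does not affect testing.

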Outcome(s): Assess the proportion of patients enrolled in the study who underwent germline testing to the proportion of patients who did not enroll in the study. Assess the effect of a patient educational program on increasing germline genetic testing rate among adult prostate cancer patients who are recommended to receive germline testing per NCCN guidelines. .

Sample Size Estimations: Target accrual is 50 patients in 12 months.

Statistical Analysis: For the primary endpoints of feasibility of implementing an educational intervention, this will be assessed by the accrual rate over 12 months. For the endpoint of efficacy of the intervention in improving rates of germline testing, the proportion of patients who undergo germline testing in this study will be compared to the proportion of patients who undergo germline testing who were eligible, but not enrolled into this study during the study time period.

AMENDMENT HISTORY

Date	Section of study protocol	Amendment or update	Reason
		N/A	

MILESTONES

Milestone	Planned date
Finalize survey instruments	July 2021
Finalize Redcap database along with CRFs	August 2021
Hiring of clinical research coordinator	August 2021
Completion of video	September 2021
Training of research coordinator	August- September 2021
Start of accrual	October 2021
6-month assessment of accrual	April 2022
Database lock	October 2022 (or sooner if 50 patients are accrued)
Analysis	November 2022
ASCO Abstract	January 2023
First Manuscript	March 2023

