3. METHODOLOGY

3.1 Study Design – General Aspects

We will then screen genitourinary oncology clinics at UC San Diego Health System to identify patients who are eligible for germline testing. After approval from their treating physician, we will approach patients in the clinic and introduce the educational intervention, which will consist of a one-on-one in-person educational sessions reviewing the rationale and the risks and benefits of germline testing. A virtual educational session was added due to the COVID-19 pandemic and will ideally occur over the Epic video chat platform, Doximity video chat, but can also occur via telephone for patients who are unable to use video chat.

The educational intervention will occur with a clinical research coordinator who will be trained to educate on germline testing in prostate cancer. At the start of the session, the patient will be given a short questionnaire (Appendix A) to assess their understanding about germline and genetic testing, along with a Family History questionnaire (Appendix B). Following this, the session will then include a one-on-one review of an educational handout on germline testing in prostate cancer (Appendix E). The handout will provide a concise, yet comprehensive review of germline testing including:

1. Overview of genetic germline testing
2. Rationale for germline testing in prostate cancer
3. Implications of germline testing in terms of patient's clinical care
4. Implications to family
5. Overview of results including discussion of pathogenic germline mutation and variants of unknown significance
6. Discussion of benefits and risks of testing

Session Overview	
Time (approximately)	Objective
1-5 minutes	Introduction
10 minutes	Pre-intervention survey
5 minutes	Video
10 minutes	Review of brochure
5 minutes	Time for patient to ask questions
10 minutes	Post-intervention survey

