4.3 Other Variables and Covariates

We will capture the following additional demographic, clinical, and disease variables:

- Demographic data: Age, Marital Status, Race, Ethnicity, Employment Status, Clinician, Primary Language, Country of Birth, Education Level.
- Previous medical history: Comorbidities, Smoking History, and Family History of Malignancies.
- Disease characteristics: Date of Diagnosis, Site of Disease, Site(s) of Metastasis, if applicable, Histology/Grade/Pathologic Parameters, PSA, Stage, Somatic Molecular Profile, Date of Collection of Tissue Analyzed, Type of Tissue Analyzed.
- Treatment data: Date of Surgery, Date of Radiation, Dose of Radiation, Systemic Therapy.
- Treatment outcomes data: Toxicity, Dose Reduction, Reason for Dose Reduction, Response, Progression, Survival.

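### The primary comparison ignores the treating clinician, so its false-positive rate can exceed 5% if both testing rates and enrolled shares differ between clinicians

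*Combined protocol and SAP*

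**What the plan says.** The second primary hypothesis (Section 2.1) is directional: "We hypothesize that the rates of germline testing among patients recruited to the study will be higher than rates of testing among patients not enrolled". Section 4.5.1 tests it with a single pooled procedure: "The proportion of patients who underwent germline testing in the intervention vs non-intervention cohorts will be compared using Fisher's exact test". It gives no significance level, power, stratification or adjustment. The two cohorts' characteristics are also compared, but nothing is said about what follows if they differ.

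The clinician enters on both sides of that comparison.

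- **Cohort membership.** Section 3.1: "After approval from their treating physician, we will approach patients in the clinic and introduce the educational intervention". The informed consent text in Section 5.1.2 repeats this as an authorisation. Eligible men who are never approached join the comparison cohort (Sections 3.2 and 4.1.2), as do men who decline.
- **Usual care.** Section 4.1.2, on the comparison cohort: "In this context, germline testing education will be at the discretion of the treating medical team".

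Section 4.3 lists the clinician among the captured variables: "Demographic data: Age, Marital Status, Race, Ethnicity, Employment Status, Clinician, Primary Language". No analysis in Section 4.5 stratifies by it or adjusts for it.

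**The concern.** Fisher's exact test treats every man in a cohort as having the same chance of being tested, independently of the others. Men seen by the same clinician may be more alike than that. A clinician who withholds approval supplies comparison men only, while one who approves freely supplies most of the enrolled men. If those clinicians also differ in how readily their patients get tested, the 2×2 table mixes the effect of education with differences between clinicians.

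This is the only inferential test of the effectiveness objective. A difference caused by which clinicians' patients enrolled could be read as an effect of the session. If higher-testing clinicians also enrol more, the error favours the study hypothesis.

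**Working it through.** **The plan's own figure.** The only quantitative statement is: "A sample size of 50 patients produces a two-sided 95% confidence interval on the proportion with a width ranging from 0.27 to 0.29", for observed proportions of 0.3 to 0.7, with "For proportions, 95% confidence intervals will be calculated using the exact method". The Clopper-Pearson limits for x of 50 are the 2.5% quantile of Beta(x, 51−x) and the 97.5% quantile of Beta(x+1, 50−x). At x = 15 they are 0.1786 and 0.4461, width 0.2675; x = 35 gives the same width. At x = 25 they are 0.3553 and 0.6447, width 0.2895. The stated range reproduces. It concerns one proportion and says nothing about the between-cohort test.

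**Inputs.** From the documents: 50 enrolled men. Assumed, because the documents are silent: two-sided 0.05, number of clinicians, number of eligible men, mean testing rate p = 0.40, and within-clinician correlation (ICC).

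**When clinician matters.** Let clinician k have testing rate p_k, e_k enrolled men and c_k comparison men, with totals n1 and n0. With no education effect, the expected difference between cohorts is Σ d_k·p_k, where d_k = e_k/n1 − c_k/n0. If every d_k is zero, clinician differences cancel. Otherwise, with rates unrelated to enrolment, the variance of the difference is approximately

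ICC·p(1−p)·Σd_k² + (1−ICC)·p(1−p)·(1/n1 + 1/n0),

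whereas the pooled test in effect uses p(1−p)(1/n1 + 1/n0).

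**Hand example.** Take 240 eligible men, six clinicians with 40 each, n1 = 50, n0 = 190, ICC 0.10. The pooled variance is 0.24 × (1/50 + 1/190) = 0.00606, and the within-clinician part is 0.9 × 0.00606 = 0.00546.

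- *All six approve equally.* Σd² = 0, ratio 0.90, effective cut-off 1.96/√0.90 = 2.07, false-positive rate about 3.9%.
- *Two withhold approval.* Approving clinicians: d = 12.5/50 − 27.5/190 = 0.105. Withholding: d = −40/190 = −0.211. Σd² = 4(0.105²) + 2(0.211²) = 0.133. Added variance 0.024 × 0.133 = 0.00319. Ratio (0.00546 + 0.00319)/0.00606 = 1.43, cut-off 1.64, rate about 10%.
- *Three withhold.* Every |d| is 0.211, Σd² = 0.266, added variance 0.00638, ratio 1.95, cut-off 1.40, rate about 16%.

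Simulation of the same three cases with Fisher's test gave about 4%, 9.5% and 15.6%. If it is the lowest-testing clinicians who withhold, the last two rise to 21% and 42%. That is confounding, not only extra variance.

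**Wider simulation.** No education effect, ICC 0.10, 5 or 8 clinicians, 200 or 400 eligible men, 50 enrolled, beta-distributed clinician testing rates with mean 40%, log-normal enrolment weights:

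| Enrolled share by clinician | Fisher rejects at 5% |
|---|---|
| Equal or mildly uneven (log SD 0 to 0.3) | about 4–6% |
| Moderately uneven (log SD 0.75) | about 8–9% |
| Very uneven (log SD 1.5) | about 15% |
| Moderately uneven, correlated 0.5 with testing habit | about 12–13% |

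Individual settings scatter by a few points around these values. A different set-up (mean testing 30%, 50 or 150 comparison men) gave 0.018–0.048 with equal shares at ICC 0.05 to 0.20. At ICC 0.10 it gave 0.054–0.070 with mildly uneven shares and 0.067–0.131 with very uneven shares.

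**The alternative.** A Cochran-Mantel-Haenszel test stratified by clinician rejected in about 4–6% in every scenario (0.017–0.038 with a continuity correction). The information it keeps is Σ(e_k·c_k/T_k) ÷ (n1·n0/N), where T_k = e_k + c_k and N = n1 + n0. With two of six withholding: 4 × 12.5 × 27.5/40 = 34.4, against 50 × 190/240 = 39.6. That is 87% kept, so an interval 1/√0.87 = 1.07 times as wide.

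**The case against.** A reader might infer that, because men are clustered within clinicians, the Fisher p-value is necessarily too small. The documents do not support that. Clustering alone does no harm when clinicians contribute to both cohorts in similar proportions; the rate then stays at or below about 5–6%, even at ICC 0.20. Inflation needs two conditions together, variation in testing between clinicians and unequal enrolled shares, and the documents establish neither.

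The text also points partly the other way. Section 4.6.1 rotates screening across clinics, Section 4.6.3 plans to offer the study to all eligible men in all genitourinary oncology clinics, and Section 1.2 promises guideline education for all the oncologists and urologists, which may narrow differences between them. Section 4.1.2 leaves education, not testing itself, to the team's discretion; that this affects who is tested is a reasonable inference, not a stated fact. The cohort comparison of characteristics might include clinician and so reveal an imbalance. Finally, this is a pilot sized for the precision of one proportion.

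All of this stands, and it makes the point conditional. It does not close it. Rotation evens out who is screened, not who is approved or who consents. Seeing an imbalance is not adjusting for it. Nothing in the plan balances or reports enrolment by clinician.

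**Conclusion.** The point holds conditionally. The pooled test takes no account of a factor that controls the approach to patients and may influence usual-care testing. If testing rates and enrolled shares both vary by clinician, the comparison can be confounded and its error rate can exceed 5%. At an assumed ICC of 0.10 the inflation is nil to slight with near-equal shares and reaches roughly two to three times nominal when shares are clearly uneven or track testing habit. ICC, clinician count, eligible numbers, testing rate and enrolment split are all assumptions, so the real size cannot be stated. This is an inexpensive improvement to the one test of effectiveness; the planned p-value has not been shown to be wrong.

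Stratifying addresses clinician only. Men who decline are part of the comparison cohort, and their self-selection would remain. The 4–6% error rate of the stratified test was obtained without such selection, so it does not show that the comparison is valid in every respect.

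**What to change.** In Section 4.5.1:

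1. Make a clinician-stratified comparison the main between-cohort analysis: an exact conditional or Cochran-Mantel-Haenszel test, with a Mantel-Haenszel risk difference and 95% confidence interval. A design-effect correction alone would not remove confounding by clinician.
2. Assign each man, in both cohorts, to one treating clinician by a rule fixed before testing outcomes are examined, and state in advance how small clinician strata will be pooled.
3. Report eligible, enrolled and tested men by clinician, so that readers can see whether shares were uneven.
4. Keep the pooled Fisher result as descriptive.
5. State the significance level and sidedness of the comparison.

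The cost is SAP wording and making sure that clinician is recorded for comparison men too; it is already a listed variable. Clinicians with only enrolled or only comparison men drop out of the stratified contrast. The information lost is about 2–12% in ordinary cases, making intervals about 1–7% wider (1/√0.98 = 1.01; 1/√0.88 = 1.07). It is about 20–30% if enrolment is very uneven, making intervals about 12–20% wider (1/√0.80 = 1.12; 1/√0.70 = 1.20).
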